8.8.4 Night-Time Sleep Respiration

Respiration will be captured by the device for the duration of the subject’s night of sleep.

8.8.5 Removal of the Respiration Reference Device

The Respiration Reference Device will be removed as prescribed in Section 5.0, following the manufacturer’s IFU after the subject arises from bed.

8.8.6 Sensor Adhesion Assessment

On Day 1, prior to removal of the first set of sensors, and after 24 hours of sensor wear for the four body locations, clinical staff will rate the skin adhesion using a 5-point scale (0-4, refer to Table 3)⁷.

Adhesion will be scored by clinical staff based on visual observation and assessment of total unpeeled surface immediately prior to Sensor removal.

8.8.7 Sensor Removal

After at least 24 hours of wear, the clinician will remove Sensors from the chest, thigh, shank, and forearm as prescribed by the BioStamp nPoint system IFU.

8.8.8 Safety and Tolerability Assessment

Safety and tolerability will be assessed immediately by the clinical staff after the Sensor's removal based on qualitative (visual observations) assessments of skin redness.

Skin irritation will be assessed on a 0 to 3 scale based on native assessments (visual observations) of skin irritation using the following scale⁸ (Table 9).

Table 9: Irritation Rating Scale

| Score | Rating | Description |
|-------|------------------------------|---|
| 0 | No reaction | --- |
| 1 | Weakly positive reaction | usually characterized by mild erythema and/or dryness across most of the treatment site |
| 2 | Moderately positive reaction | usually distinct erythema or dryness, possibly spreading beyond the treatment site |
| 3 | Strongly positive reaction | strong and often spreading erythema with edema and/or eschar formation |

8.8.9 Data Download

Site staff will download the data from and recharge the BioStamp nPoint chest and thigh sensors using the Link App. The sensors will not be used again.

Site staff will download the Heart Rate Reference Device data to a dedicated study computer at the end of the wear period using the manufacturer's proprietary software per the instructions for use.

Site staff will download the Respiratory Reference Device data after each night of sleep to a USB stick following the manufacturer's instructions for use.

8.8.10 Subject Training – Remote Kit

The subject will be trained on the BioStamp nPoint system subject IFU and the Link App operations to be performed under observation, defined in Section 8.9. While observed by the clinician, the subject will then apply the sensors to the chest and thigh using the Link App, and will conduct and annotate the activities in Table 8 using the Link App prior to departure from the clinic. The clinician will evaluate adhesion using the scale in Table 3 and observe the subject through re-applying any Sensors with a non-zero score for up to two applications. If two non-zero scores are noted, the clinician should then apply the Sensor.

8.9 Study Assessments – Remote (Unobserved)

After the completion of the supervised evaluation period, subject training, and replacement of BioStamp nPoint sensors on Day 1, the subject will remain in the clinic, where they will continue to wear the BioStamp nPoint system and the Heart Rate Reference Device and execute Table 8 activities.

8.10 Study Assessments – In Clinic – Visit 2 (Supervised)

On the same day (Day 1), the subject will go to bed. Upon waking, clinical site staff will observe the subject removing, cleaning, synchronizing, and beginning to recharge the BioStamp nPoint sensors. Sensor safety and tolerability will then be assessed.

8.10.1 Night-Time Sleep Duration

When the subject goes to bed (lights out) and arises from bed (woken by site staff) the sleep onset time and wake time will be recorded by site staff on the CRF. Subjects will be observed throughout the night to annotate on the CRF any periods of wakefulness between these times

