4.0 STUDY ENDPOINTS

4.1 Effectiveness Endpoints

The effectiveness endpoints for this study are the various types of measurements made by the BioStamp nPoint system. All effectiveness endpoints to be statistically summarized will be collected using the BioStamp nPoint during in clinic supervised use. The effectiveness endpoints are as follows:

- Heart Rate (bpm)
- Heart Rate Variability (RMSSD³ (msec) and LF/HF Ratio⁴)
- Respiration (average respiration rate)
- Activity Classification (activities – sleep, standing, sitting, lying, walking and other)
- Activity Parameters - total step counts in a 6 minute walk test
- Sleep (sleep onset time (hours, minutes, and seconds), sleep wake time (hours, minutes, and seconds))
- Posture Classification (sleep posture, stationary posture standing, stationary posture sitting)

For each endpoint, the BioStamp nPoint measurements will be compared to a similar FDA-cleared measurement device, other measurement devices, or independent observer measurements. The FDA-cleared measurement devices used as comparators for this study are the Actiheart heart rate reference device and the Capnostream portable respiratory monitor.

Table 1 displays the comparator method for each endpoint category.

Table 1: Endpoint Variable Group and Measurement Comparator

| Index | Endpoint Variable Group | Measurement Comparator |
|-------|-------------------------|-----------------------------|
| 1 | Heart Rate | Actiheart Device |
| 2 | Heart Rate Variability | Actiheart Device |
| 3 | Respiration | Capnostream Device |
| 4 | Activity Classification | Independent Observer |
| 5 | Activity Parameters | Manual Step Counting Device |
| 6 | Sleep Parameters | Independent Observer |
| 7 | Posture | Independent Observer |

³ RMSSD: root-mean-square of successive difference of the time intervals between successive heartbeats.

⁴ LF/HF ratio: the ratio of power in the low-frequency (LF, 0.04-0.15 Hz) and high-frequency (HF, 0.15-0.4 Hz) bands of heart rate variability in the frequency domain.

Individual independent observers will receive training on the operation of all devices and execution of the study protocol before the enrollment of any subjects.

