8.8.3 Night-Time Sleep Duration

When the subject goes to bed (lights out) and arises from bed (woken by site staff), the sleep onset time and wake time will be recorded by site staff on the CRF. Subjects will be observed throughout the night to annotate on the CRF any periods of wakefulness between these times.

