11.3 Effectiveness Variables

The effectiveness endpoints for this study are the various types of measurements made by the BioStamp nPoint system. All effectiveness endpoints to be statistically summarized will be collected using the BioStamp nPoint during the supervised-use phase. The effectiveness endpoints are as follows:

- Heart Rate (bpm)
- Heart Rate Variability (RMSSD⁵ (msec) and LF/HF Ratio⁶)
- Respiration (average respiration rate)
- Activity Classification (activities – standing, sitting, lying, walking and other)
- Activity Parameters - total step counts in a 6 minute walk test
- Sleep (sleep onset time (hours, minutes, and seconds), sleep wake time (hours, minutes, and seconds))
- Posture Classification (sleep posture, stationary posture standing, stationary posture sitting)

For each endpoint, the BioStamp nPoint measurements will be compared to a similar FDA approved measurement device, to other basic or manual measurement devices, or to independent observer measurements. The FDA approved measurement devices for this study are the Actiheart heart rate reference device and the Capnostream portable respiratory monitor. Table 10 displays the comparator method for each endpoint category.

Table 10: Endpoint Variable Group and Measurement Comparator

| Index | Endpoint Variable Group | Measurement Comparator |
|-------|-------------------------|-----------------------------|
| 1 | Heart Rate | Actiheart Device |
| 2 | Heart Rate Variability | Actiheart Device |
| 3 | Respiration | Capnostream Device |
| 4 | Activity Classification | Independent Observer |
| 5 | Activity Parameters | Manual Step Counting Device |
| 6 | Sleep Parameters | Independent Observer |
| 7 | Posture | Independent Observer |

Individual independent observers will receive training on the operation of all devices and execution of the study protocol before the enrollment of any subjects.

For heart rate and heart rate variability, the values collected will be the one minute average heart rate, the one minute RMSSD, and the five-minute LF/HF ratio from the BioStamp nPoint and the one minute average heart rate, the one minute RMSSD, and five minute LF/HF from the Actiheart device on each of six recording times for each subject. Two readings will be taken while the subject is at rest, two while exercising and two while lying down. These readings will be collected during the activities listed in Table 7 and Table 8.

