For respiration rate, the average resting respiration rate values will be collected at one minute time intervals during sleep on each subject using both the BioStamp nPoint and the Respiration Reference Device.

For the activity classification variable, each subject will be presented with five tasks (standing, sitting, lying, walking and stationary bike riding) in varied order and the activity classification will be recorded by the BioStamp nPoint and by the independent observer. This procedure will be repeated five times for each subject.

⁵ RMSSD: root-mean-square of successive difference of the time intervals between successive heartbeats.

⁶ LF/HF ratio: the ratio of power in the low-frequency (LF, 0.04-0.15 Hz) and high-frequency (HF, 0.15-0.4 Hz) bands of heart rate variability in the frequency domain.

For the exercise parameter “number of steps taken”, the number of steps taken by the subject during a 6 minute walk test will be recorded using both the BioStamp nPoint and a simple step counting device. This procedure will be repeated five times for each subject.

For the sleep parameters sleep onset time and wake time, the BioStamp nPoint values and independent observer values will be collected on each night and morning at the study site.

Posture classification variables will be analyzed separately for each type of posture activity (sleep positions, stationary posture standing and stationary posture sitting). For a given posture activity, the posture classification will be recorded by the BioStamp nPoint and the independent observer for two repeats each of each ground-truth posture for each subject. Each repeat will generate 5 independent observations of posture. The posture classifications for each posture classification variable are given in Table 11.

Table 11: Posture Variable vs Classification

| Index | Posture Variable | Posture Classification |
|-------|-----------------------------|---|
| 1 | Simulated sleep positions | Supine, prone, left side and right side |
| 2 | Stationary Posture Standing | Upright, lean left, lean right, lean back, lean forward |
| 3 | Stationary Posture Sitting | Upright, lean left, lean right, lean back, lean forward |

Sensor adhesion to the subject will be measured on a 4 point scale by the independent observer for each of four sensor patches on each subject following 24 hours of continuous wear. The adhesion rating scale is presented in Table 3.

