11.6.2 Effectiveness Endpoint Analyses

For pairs of measurements collected on the continuous scale (quantitative to quantitative comparisons), scatter plots with the 45 degree line of agreement superimposed will be constructed from paired observations from the two sources (BioStamp nPoint vs comparator) along with Bland-Altman plots of the data. The mean absolute error (MAE) and the root-mean-square error (RMSE) estimates of agreement will be calculated for each comparison. The standard deviations of each of the agreement measures will also be computed.

For pairs of measurements collected on a categorical scale (qualitative to qualitative comparisons), two-way tables of agreement will be constructed for each comparison. The agreement percentage will be computed for each table.

The number and percentage of sensor patches in each category of the adhesion scoring scale will be tabulated.

The statistical analyses of the effectiveness data will also be described in the Statistical Analysis Plan (SAP) for the study. The SAP will be written and finalized prior to database lock.

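### The sleep endpoint scores the device against bedtime and staff-imposed rising, and the protocol names no analysis of the wake periods observed in between

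*Protocol*

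**What the plan says.** The reference times are fixed in two places. For night one, 8.8.3 Night-Time Sleep Duration says that when the subject goes to bed at lights-out and "arises from bed (woken by site staff), the sleep onset time and wake time will be recorded by site staff on the CRF". For night two, 8.10.1 gives the same rule: "arises from bed (woken by site staff) the sleep onset time and wake time will be recorded by site staff on the CRF". Both sections then add: "Subjects will be observed throughout the night to annotate on the CRF any periods of wakefulness between these times".

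The endpoint is narrower than what is collected. Section 11.3, like 4.1, defines it as "Sleep (sleep onset time (hours, minutes, and seconds), sleep wake time (hours, minutes, and seconds"). On data collection it says: "For the sleep parameters sleep onset time and wake time, the BioStamp nPoint values and independent observer values will be collected on each night". Table 1 and Table 10 name the independent observer as comparator. For continuous pairs, 11.6.2 specifies scatter and Bland-Altman plots and adds: "The mean absolute error (MAE) and the root-mean-square error (RMSE) estimates of agreement will be calculated for each comparison".

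Section 4.1 also lists sleep among the activity classes: "Activity Classification (activities – sleep, standing, sitting, lying, walking and other"). The matching list in 11.3 leaves sleep out. Section 2.0 names sleep, and respiration during sleep, among the metrics that the algorithm package delivers.

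**The concern.** The primary objective is the accuracy of the algorithm measurements, and sleep is a declared effectiveness endpoint in a study meant to support a 510(k) submission. A reader of the results will take a small error in sleep onset and wake time as evidence that the device recognises sleep and waking. As written, both reference times mark bed events: lying down at lights-out, and rising when roused. Agreement with them shows that the device can tell when the subject is in bed.

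The only reference information on natural transitions between sleep and wake is the CRF annotation, and the protocol gives it no analytic role. The reference rule can also work against a good algorithm, because one that correctly waits for sleep to begin, or notices waking before staff come, departs from the recorded times.

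**Working it through.** **1. Nothing to reproduce.** The protocol gives no margin, standard deviation or acceptance limit for sleep. It does fix the number of pairs: 25 subjects × 2 nights = 50 per clock time (60 if the 5 additional subjects are enrolled).

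**2. Errors under the written rule.** For one subject-night let B = lights-out, S = true sleep onset, W = true final waking and R = rising when woken, with B ≤ S < W ≤ R. The reference is (B, R). With device outputs d₁ and d₂, the scored errors are d₁ − B and d₂ − R.

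- A device that labels all time in bed as sleep has d₁ = B and d₂ = R, so its errors are 0 and 0.
- A device that is exactly right has d₁ = S and d₂ = W, so its errors are S − B (the sleep latency) and −(R − W) (the lead before staff arrive).

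If latency, or the lead before staff, were 10 minutes on every night, the exactly right device would have MAE = RMSE = 10 minutes on that time. At 30 minutes it would have 30. The in-bed labeller would have 0. These minutes are assumptions; the direction follows from the rule.

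**3. What happens between the two times.** Neither error has a term for wakefulness between S and W. As an illustration, assume 480 minutes in bed, final-wake error with SD 3 minutes, 50 subject-nights, and the same error draws for two devices: one detects all mid-night waking and one detects none. Wake-time MAE is 2.13 minutes and RMSE 2.80 minutes for both, at every amount of waking. The equality holds by construction. The particular values depend on the assumed SD and the draw.

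Scoring the annotated time by minute would separate the two. For the blind device, agreement = 1 − (minutes awake / 480):

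| Minutes awake (assumed) | Overall agreement | Wake time detected | Sleep overstated by |
|---|---|---|---|
| 15 | 96.9% | 0% | 15 min |
| 30 | 93.8% | 0% | 30 min |
| 60 | 87.5% | 0% | 60 min |
| 90 | 81.3% | 0% | 90 min |

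With 6 to 8 hours in bed and 20 to 60 minutes awake, agreement runs from 1 − 60/360 = 83.3% to 1 − 20/480 = 95.8%. Over 50 nights that is 50 × 20 = 1,000 to 50 × 60 = 3,000 observed wake minutes. Overall agreement stays high although no waking is detected, so wake and sleep time must be reported separately.

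**4. Whether another endpoint fills the gap.** The five scored activity tasks (4.1, 11.3) are standing, sitting, lying, walking and cycling, all done awake. Sleep position is assessed in awake subjects (4.1). Respiration is compared during sleep (4.1, 11.3), but the protocol does not say how sleeping minutes are identified, and restricting the respiration data to them would not test wake detection.

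**The case against.** The strongest reply is that only the protocol is at hand. Section 11.6.2 says that the SAP will also describe the effectiveness analyses, and a SAP could use the annotations to adjust onset and wake time, to select sleeping minutes for respiration, or to score the sleep activity class listed in 4.1. A reader might infer that the annotations enter no analysis at all; the documents do not establish that. They show only that the protocol names none. What stands is that 4.1 and 11.3 fix the endpoint and that 8.8.3 and 8.10.1 fix the reference rule.

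Second, the Indications for Use name no detection of night waking, wake after sleep onset or total sleep time, and the documents do not say that the device gives a sleep/wake output through the night. A reader might infer that the trial fails to support a claim it makes about night waking. That inference is not supported; the point limits what can be concluded from the sleep endpoint.

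Third, it is tempting to add that nobody wakes the wearer in real use, or that a staff-imposed awakening is easy for the sensor to detect. The stated use includes healthcare settings, where staff may well wake a patient, and the documents say nothing about ease of detection. The point needs neither argument.

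Fourth, the rule could be read loosely, with observers judging true onset rather than noting lights-out. That would remove the latency problem but not the missing analysis of waking between the two times. The literal reading also fits the text better, since wakefulness is to be noted between these two recorded times.

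Finally, an observer can miss someone lying quietly awake. This is a fair limit on the remedy, but the protocol already accepts the observer as its sleep comparator.

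**Conclusion.** The point holds as a limit on the sleep endpoint and should be corrected. Under the written reference rule, MAE and RMSE of onset and wake time cannot distinguish sleep/wake detection from detection of being in bed, and they count some correct detections as error. This follows from the definitions and needs no assumed figure.

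The size is illustrative only. Time in bed, minutes awake, latency and the 3-minute SD are all assumed, and the population excludes people with sleep disorders or insomnia. A reader might take the 83% to 96% agreement range as a forecast of a trial result, but it belongs to a minute-level analysis that the protocol does not plan. Nothing here invalidates the other endpoints.

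**What to change.** In 11.3 and 11.6.2:

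- Use the annotated wake periods to set the observer's reference sleep onset and final wake time, and align the wording of 8.8.3 Night-Time Sleep Duration and 8.10.1 with that.
- Add a two-way sleep/wake table for both nights at the device's output resolution. Report separately the percentage of observer-wake time and of observer-sleep time that the device classifies correctly, summarised by subject.
- Reconcile this with the sleep activity class that 4.1 lists and 11.3 omits.
- If the device gives no sleep/wake output between onset and wake, label the existing results as agreement with bedtime and staff-imposed rise time, and limit the sleep conclusion to that.

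The cost is one extra table from data already being collected, and probably a less favourable figure than the clock-time errors. The observer reference remains imperfect for quiet wakefulness, and the report should say so.

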8.10.2 Night-Time Sleep Respiration

When the subject is ready to go to sleep, site staff will place the Respiration Reference Device on the subject as described in Section 5.0, following the manufacturer's IFU. Respiration will be captured by the device for the duration of the subject's night of sleep. After the subject wakes, the Respiration Reference Device will be removed as prescribed in Section 5.0, following the manufacturer's IFU.

8.10.3 Sensor Removal

On the morning of Day 2, while observed by the site staff, the subject will remove sensors from the chest and thigh, and will clean them, synchronize the recorded data, and begin to recharge the sensors as prescribed by the BioStamp nPoint system IFU.

8.10.4 Safety and Tolerability Assessment

Safety and tolerability will be assessed immediately by the clinical staff after the Sensor's removal based on qualitative (visual observations) assessments of skin redness level.

Skin irritation will be assessed on a 0 to 3 scale based on native assessments (visual observations) of the skin sensor locations using the scale⁹ located in Table 9.

8.10.5 Equipment Return

The Heart Rate Reference Device will be removed. The subjects will return the provisioned equipment; equipment return will be documented on the Device Accountability Form.

8.10.6 Usability Survey

Subjects will complete a survey related to the intuitiveness and ease of use of the BioStamp nPoint system.

8.11 Data Download

The clinical staff will verify that the data from the BioStamp nPoint system has successfully been uploaded to the BioStamp nPoint cloud, and will download the data from the Heart Rate Reference Device and the Respiration Reference Device after the system is returned on Day 2. Algorithm outputs will be derived from the Web Portal.

8.12 Subject Follow-up

A Safety follow-up telephone call will be made between Day 3 and Day 5 to assess for adverse events associated with study participation.

9.0 Completion or Early Withdrawal of Subjects

9.1 Subject Completion

Completion of the study is defined as:

1. completing the supervised activities;
2. wearing the sensors for two days;
3. returning the sensors to the coordinators;
4. completing the usability survey;
5. completing the follow-up telephone call.

9.2 Subject Early Discontinuation / Withdrawal of Subjects

Subjects are free to withdraw from the study at any time, without prejudice. Subjects should be withdrawn from the study if any of the following events occur:

1. Subject develops an illness or any other condition or event that would interfere with his/her continued participation;
2. Subject is noncompliant with the study procedures, or unable to continue in the opinion of the Investigator;
3. Subject withdraws his/her consent;
4. The Sponsor or a regulatory agency requests withdrawal of the subject.

Investigators should attempt to obtain information on subjects, in the case of withdrawal or discontinuation. For subjects considered as lost to follow-up, the Investigator should make an effort (at least 1 phone call to the subject on each of 2 separate days), and document his/her effort (date and summary of the phone call in the source documents) to complete the final evaluation. All results of these evaluations and observations, together with a narrative description of the reason(s) for discontinuing the subject, must be recorded in the source documents. The Study Termination Case Report Form (CRF) must document the primary reason for withdrawal or discontinuation.

